#### 1.2.2 Work-package 2 objectives

The aim of this work-package is to highlight current guidelines for CDI diagnosis and treatment, at both European and national levels, and measure compliance with these. We will also measure the impact of CDI on healthcare systems, and determine if better compliance with guidelines leads to a

lower burden in terms of reducing cases and costs. Objectives and deliverables for WP2 will be closely aligned with those for WP1, using a synergistic approach to study design (see Figure 1). The timing of the objectives has been planned so that data and analyses generated from WP1 will be available for analyses in the required objectives in WP2. In addition, much of the analysis in the cost-effectiveness objective will be based on data generated from earlier objectives within WP2; the timing of these two objectives (O2.5 and 2.6) has therefore been planned accordingly.

Objective 2.1	To highlight current guidelines for disease detection, notification and management/control
Objective 2.2	To determine the heterogeneity in testing density and in following the existing guidance (including identification of missed diagnoses and empiric treatment approach practices)
Objective 2.3	To determine the heterogeneity in current surveillance practices and ways to improve them.
Objective 2.4	To describe current treatment pathways for patients with CDI infection and recurrences.
Objective 2.5	To elucidate the overall costs of CDI, including management of multiples episodes and re-hospitalisation (healthcare perspectives incl. indirect financial impact on the healthcare system).
Objective 2.6	To measure the impact of CDI management on the healthcare system and the impact of current control measures (infection control/antibiotic stewardship).

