## 6.3. Study period and important time points.

The study period is June 2018-June 2019.

The index date for the cases is defined as the date of the stool sample collection (either June/July 2018 or Oct/Nov 2019).

The index date for the controls is defined as the date of the stool sample collection either June/July 2018 or Oct/Nov 2019).

Queries within the CRF relate to that patients episode, with reference to the six months prior and six months subsequent to the index sample.

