#### 7.2 Univariate analysis

Univariate analysis will be used to assess outcomes and risk factors; continuous variables will be compared between cases and controls by t-test; categorical variables will be compared between cases and controls by chi-squared (fishers exact where numbers are below 5). Risk ratios (Odds ratio if it is case control study) will be calculated for CDI cases with identified variables of interest. Univariate analysis will be used to assess consistency between countries and between different healthcare settings.

The variables to be included in the univariate analysis are shown in the table in appendix 1.

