7.1.1	If yes please	Name of	Univariate/multivariate	Patient admission
	complete the table	drug is		when the sample
	below	Categorical	Univariate/multivariate	was taken
		Number of		
		dates of	Univariate/multivariate	
		treatment is		
		Continuous	Univariate/multivariate	
		Indication is		
		Categorical		
		Route is		
		Categorical		
7.2	Did the patient	Binary	Univariate/multivariate	Patient admission
	require			when the sample
	change/escalation			was taken
	of surgical			
7.2.1	If ves please	Name of	Univariate/multivariate	Patient admission
	complete the table	drug is		when the sample
		Categorical	Univariate/multivariate	was taken
		Number of		
		dates of	Univariate/multivariate	
		Continuous	Univariate/multivariate	
		Continuous		
		Indication is		
		Categorical		
		Route is		
0.6		Categorical		
8. Surgery				

8.1	Has the patient had	Binary	Univariate/multivariate	Up to 12 weeks
	12 wooks proceeding			previous to the
	12 weeks preceding			sample
011		Dinorry		Un to 12 weaks
8.1.1	If yes was it Elective	Віпагу	Univariate/multivariate	Up to 12 weeks
	or Acute			previous to the
0.1.0				sample
8.1.2	Please complete	Type of .	Univariate/multivariate	Up to 12 weeks
	table	surgery is		previous to the
		Categorical	Univariate/multivariate	sample
		Number		
		Number of		
		days		
		between		
		surgery and		
		sample is		
		Continuous		
9. GI Inter	ventions			
9.1	Has the patient had	Binary	Univariate/multivariate	Up to 12 weeks
	any Gi			previous to the
	Interventions or			sample
	diagnoses in the 12			
	weeks preceding			
	the index sample			
9.1.1	If yes please	Туре от	Univariate/multivariate	Up to 12 weeks
	complete the table	intervention		previous to the
		IS Colored in al		sample
		Categorical	Univariate/multivariate	
		Number of		
		Number of		
		uays		
		between		
		intervention		
		Continuous		
10 Outcor	nes	continuous		
If the sample was taken as a hernital				
inpatient		pical		
10.1	During the 30 davs	Binarv	Univariate/multivariate	Up to 30 davs
	after the sample	, ,	,	after the index
	was the patient.			sample
	was the patient	Continuous	Univariate/multivariate	· · · ·
	discharged	(no. of		
		davs)		
10.2	Was the patient re-	Binarv	Univariate/multivariate	Up to 30 days
	admitted	,		after the index

				sample		
10.2.1	If yes, please give	Continuous	Univariate/multivariate	Up to 30 days		
	the dates of	(no. of		after the index		
	subsequent	days)		sample		
	hospital admissions					

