10.3	If the sample was	Binary	Univariate/multivariate	Up to six months		
	taken as a hospital	-		after the index		
	inpatient, was the			sample		
	patient discharged	Continuous	Univariate/multivariate			
	>30 days after the	(no. of				
	sample	days)				
If the sam	ple was taken as a con	nmunity				
patient	•	-				
10.4	Was the patient	Binary	Univariate/multivariate	Up to 30 days		
	admitted to			after the index		
	hospital			sample		
10.4.1	If yes, please give	Continuous	Univariate/multivariate	Up to 30 days		
	dates of the	(no. of		after the index		
	subsequent	days)		sample		
	hospital admissions					
If the sam	If the sample was taken as a hospital inpatient or a community patient					
10.5	Did the patient die	Binary	Univariate/multivariate	Up to 30 days		
	in the 30 days after			after the index		
	the sample			sample		
		Continuous	Univariate/multivariate			
		(no. of				
		days)				
10.5.1	If yes, was the	Binary	Univariate/multivariate	Up to 30 days		
	death linked to CDI			after the index		
				sample		
10.6	Was the patient	Binary	Univariate/multivariate	Up to six months		
	admitted to			after the index		
	hospital between			sample		
	30 days and 6					
	months after the					
	sample					
10.6.1	If yes, please give	Continuous	Univariate/multivariate	Up to six months		
	the dates of	(no. of		after the index		
	hospital admissions	days)		sample		
10.7	Did the patient die	Binary	Univariate/multivariate	Up to six months		
	between 30 days			after the index		
	and 6 months after			sample		
	sample?	Continuous	Univariate/multivariate			
		(no. of				
		days)				
10.7.1	If yes, was the	Binary	Univariate/multivariate	Up to six months		
	death linked to CDI			after the index		

		sample

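### Inpatient readmission is counted from the stool sample rather than from discharge, with no at-risk rule, so the case-control comparison is biased if length of stay or in-hospital death differs between the groups

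*SAP*

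**What the plan says.** SAP 6.3 sets the time origin: "The index date for the cases is defined as the date of the stool sample collection", and the same for controls. In section 10 of SAP Appendix 1:

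- **Items 10.1 and 10.3** record discharge within 30 days and discharge ">30 days after the" sample, each with a number of days.
- **Item 10.2**, for inpatients, begins "Was the patient re" (re-admitted). It is binary, with a window of up to 30 days after the index sample. Item 10.2.1 takes the admission dates.
- **Item 10.4** is the corresponding admission item for community patients.
- **Item 10.6**, for inpatients and community patients, records admission to "hospital between" 30 days and 6 months after the sample, with dates in 10.6.1.
- **Items 10.5 and 10.7** ("Did the patient die") record death in the same two windows, with days.

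All of these are marked for univariate and multivariate analysis. Under SAP 7.2, "categorical variables will be compared between cases and controls by chi-squared", or by Fisher's exact test for small counts. SAP 7.3 adds unconditional logistic regression. SAP 5 drops a patient from the analysis of an outcome only when its value is missing. SAP 2.5 makes comparison of outcomes between cases and controls, and between countries, a main objective.

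**The concern.** A patient in hospital is not at risk of readmission. With the window fixed at the sample, a patient discharged on day 7 contributes 23 days at risk, one discharged on day 28 contributes 2, and one still in hospital at day 30 contributes none. Someone who dies before discharge is never at risk. The time in which the event can occur is therefore set by length of stay and in-hospital death. Protocol 3.2.2 lists length of stay as a secondary outcome and mortality as the primary outcome of the same study.

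If either differs between the groups, a plain comparison of proportions mixes the readmission rate with the chance to be readmitted. A true excess in cases could shrink, vanish or reverse. Comparisons between countries with different lengths of stay would be affected in the same way. Item 10.2 applies to the hospital patients in SAP Table 1: 156 cases (83 + 49 + 24) and 365 controls. Re-hospitalisation also matters to the wider project: Protocol Objective 2.5 covers costs "including management of multiples episodes and re-hospitalisation".

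**Working it through.** The documents give no readmission rate, length of stay or in-hospital death rate, so there is no figure to reproduce. All inputs in steps 1 to 5 are assumptions chosen to show size.

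**Set-up.** Time from sample to discharge is exponential with mean m, so h = 1/m. The readmission hazard after discharge is constant and equal in both groups: λ = −ln(0.8)/30 = 0.00744 per day, that is 20% within 30 days of discharge. There are no deaths at first. The probability of a yes on item 10.2 is

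P = ∫₀³⁰ h·e^(−ht)·[1 − e^(−λ(30−t))] dt = (1 − e^(−30h)) − [h/(h − λ)]·(e^(−30λ) − e^(−30h)).

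**Step 1, main illustration.**
- Controls, m = 8: 0.9765 − 1.0633 × (0.8 − 0.0235) = 0.151.
- Cases, m = 14: 0.8827 − 1.1162 × (0.8 − 0.1173) = 0.121.
- OR = (0.1206/0.8794)/(0.1509/0.8491) = 0.77. The true value is 1.0.

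**Step 2, other mean stays in cases, controls at 8 days.**

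| Mean stay, cases (days) | OR on item 10.2 |
|---|---|
| 7 | 1.05 |
| 8 | 1.00 |
| 10 | 0.91 |
| 12 | 0.84 |
| 14 | 0.77 |
| 20 | 0.62 |

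**Step 3, a real excess.** Give cases a 25% risk within 30 days of discharge (λ = −ln(0.75)/30) and a mean stay of 14 days. Item 10.2 then shows 15.2% in cases against 15.1% in controls, so the excess disappears.

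**Step 4, deaths coded as no.** With in-hospital death of 8% in controls and 15% in cases, the step 1 figures become 0.1509 × 0.92 = 13.9% and 0.1206 × 0.85 = 10.2% to 10.3%, OR 0.71.

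**Step 5, does coding the others as missing solve it?** A second set of assumptions has a 15% risk within 30 days of discharge in both groups, mean stays of 7 and 14 days, and in-hospital deaths of 5% and 10%. Mean days at risk are 21.9 in controls and 15.9 in cases. With everyone in the denominator, item 10.2 shows 11.1% v 8.1%, OR 0.70. Restricted to patients discharged alive by day 30, the OR is still 0.84, because those discharged later in the window have less of it left.

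**The case against.** The strongest reply is that a fixed window from the sample, with everyone in the denominator, is a legitimate quantity: the crude risk of rehospitalisation after the episode. It matches the mortality time points, the index date and community item 10.4. Conditioning on live discharge has its own cost, because discharge and survival come after the sample and may be affected by CDI. This stands, and it is why the sample-anchored figures should stay as descriptive results. The SAP, however, does not say that this is the quantity it wants, and it plans to test it between cases and controls.

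Several stronger readings are tempting and are not supported:

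- **That readmission is recorded only to day 30.** Item 10.6 continues to 6 months with dates. A discharge on day 31 and readmission on day 45 is captured there. On the step 1 assumptions, readmission at any time to day 182 is 72.5% v 71.2%, OR 0.93. The stay effect is thus mostly in item 10.2, although the SAP does not say that the two items will be combined.
- **That in-hospital deaths count as not readmitted.** No text says so; they could be entered as unavailable and dropped under SAP 5. Step 4 depends on this coding, and steps 1 to 3 do not.
- **That the study expects cases to stay longer or die more often.** Protocol 3.2.2 only lists these as outcomes to compare, without direction. Controls also had unformed stools and come from the same sites.
- **That this odds ratio enters the cost model.** The cost sections describe surveillance data, micro-costing and modelling. None uses the item 10.2 comparison.

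Readmission is also not a named primary or secondary outcome in Protocol 3.2.2.

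**Conclusion.** The point holds as a gap in the definition of the analysis, not in data capture. As written, the inpatient comparison on item 10.2 has time at risk that depends on length of stay and in-hospital death, and nothing in SAP 5, 7.2 or 7.3 corrects for it. Item 10.6 has the same origin and likewise no rule for who is at risk.

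The bias is conditional. It points towards apparent protection of cases only if they stay longer after the sample or die in hospital more often. It is nil if both are equal, and slightly the other way if cases stay less long. With no deaths and controls at 8 days, the odds ratio under no true difference is about 0.9 at a mean case stay of 10 days, 0.77 at 14 and 0.62 at 20. These sizes rest on exponential stays, a constant readmission hazard and invented rates. They show that the effect can matter, not how large it is in this study. The change should be made, but no primary result depends on it.

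**What to change.** In SAP 7.2 and Appendix 1:

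1. Make the inpatient case-control comparison of readmission the first admission after live discharge, among patients discharged alive. Report it within 30 days of discharge, and as time from discharge to first readmission up to the end of the six-month follow-up, with death as a competing event. Derive it from items 10.1 and 10.3 (discharge), 10.2.1 and 10.6.1 (admissions), and 10.5 and 10.7 (death).
2. State that in-hospital deaths and patients not yet discharged are not at risk, instead of leaving them to be entered as no or as missing.
3. Report the sample-anchored 10.2 and 10.6 figures only as descriptive crude risks, beside mortality.
4. Keep the sample anchor for community patients (10.4), who are at risk from the sample date.

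The cost is SAP wording, a coding rule and one derived variable; no new data are needed. The new analysis is conditional on live discharge, so the SAP should say so and read it together with mortality. Unclear discharge or admission dates should be queried promptly, because Protocol 1.4.2 has sites destroy the patient link once verification is complete, within one month of collection.

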All data held by the study team will be pseudonymised to a study number. Only the original submitting laboratory will hold the code to link back to the participant. All samples will be sent for processing under the study number only. After 6 months the original hospital will be asked to collect health data on a pseudonymised (study number only) clinical report form on all cases and a proportion of controls (CDI negative samples) identified by the central testing laboratory. Under GDPR pseudonimised data is classified as personal data. After collection of the data and verification/data querying has been completed (within one month of collection) the link will be destroyed at the local study sites, to ensure there cannot be any link to participants, rendering the data anonymous at this point. To add a further layer of protection all participating sites are also pseudonymised, to prevent link back to the site by consortium partners. The University of Leeds will hold the link back to the site code on a password protected spreadsheet on secure University of Leeds servers during the collection of the data; this will be destroyed after data collection and will not be archived.

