#### 3.2.2 Outcome measures

Primary outcome measure: Crude mortality at 30 days and 6 months after the sample was taken will be compared between case and controls, those that received a correct diagnosis at the original hospital and those that were 'missed' (either due to lack of testing or inadequate testing) and between community and hospitalised patients.

Secondary outcome measures: Patient length of stay, severity of infection (e.g. WCC, serum albumin, temperature), need for escalation of medical/surgical care due to gastrointestinal disease, post-infectious sequelae.

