#### 3.2.6 Data collection

Data will be collected via a standardised CRF, with a full supporting SOP. The CRF will be completed by the clinical care team at the participating site that submitted the sample (during O1.1). The CRF will not contain any participant identifiable data; all data will be held against a pseudoanonymised study code, with the link back held by the clinical care team only. COMBACTE-CDI investigators will not access participant's notes or access the link back. Once the CRF data has been collected and validated and verified the link-back will be destroyed by the local study site.

Data will be collected on the following variables on outcomes of CDI;

- Evidence of other enteric pathogens (+/- 7 days of the original sample)?
- Symptoms at time of the sample
- Alternative cause for the patient's diarrhoea documented (e.g. laxatives, pathogen)?
- Duration of diarrhoea/non-normal bowel habit?
- Primary/recurrent CDI
- Antibiotics at the time of the sample or the preceding 3 months?
- Evidence of colitis?
- Evidence of post-infectious diarrhoea

- CDI Severity markers (Temperature (nearest reading +/- 3 days of the sample), serum creatinine (nearest reading +/- 3 days of the sample), White cell count (nearest test +/- 3 days of the sample)
- Treatment for CDI episode
- Was treatment for CDI/diarrhoea escalated medical/surgical?
- Outcome 30 days and 6 months after the sample (discharged, in-patient, died)
- Length of stay

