#### 3.2.7 Data analysis

Comparisons will be made between recurrence/Morbidity/Mortality (crude and attributable) rates in different healthcare settings and countries. Outcomes will also be compared for different strain types (as identified in O1.2).

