### **5.0 Reporting**

This is strictly an observational (surveillance) study. Results of additional testing will not be reported back to participating laboratories. The study is therefore 'non-interventional' as the participant samples will be processed as per local policy at each hospital and those results acted upon; i.e. additional COMBACTE-CDI study results will NOT be available for patient management.

Study reports and conclusions based on analysis of data at a national and European level will be prepared by the lead investigator for each objective.

A full study report will be presented at the end of each objective. Results will be submitted for presentations at scientific meetings followed by preparation of manuscript and publication whenever applicable. Authorship will be led by the lead investigator for each objective (see consortium agreement).

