2.7	Did the patient receive any supportive measures/domestic help by friends or relatives during the presence of CDI?	Binary	Univariate/multivariate	Patient admission when the sample was taken

2.7.1	If yes, how many hours per day?	Continuous	Univariate/multivariate	Patient admission when the sample
				was taken
2.8	Did the patient receive any supportive measures/domestic help by professionals during the presence of CDI?	Binary	Univariate/multivariate	Patient admission when the sample was taken
2.8.1	If yes, how many hours per day?	Continuous	Univariate/multivariate	Patient admission when the sample was taken
2.9	Were any CDI related purchases necessary?	Binary	Univariate/multivariate	Patient admission when the sample was taken
2.9.1	If yes, please describe below	Categorical	Univariate/multivariate	Patient admission when the sample was taken
3. Laborat	ory Testing	1	1	
3.1	Did the patient have any test for other enteric pathogens up to 7 days before or up to 7 days after the EUCLID sample was taken	Binary	Univariate/multivariate	Patient admission when the sample was taken
3.1.1	If yes please indicate test results	Categorical	Univariate/multivariate	Patient admission when the sample was taken
3.2	What was the local policy for repeat testing of patients with CDI (at the time of the sample)	Binary (repeat or not repeat)	Univariate/multivariate	Patient admission when the sample was taken
4. CDI Test	ting	ſ	ſ	
4.1	Was the patient tested for CDI due to diarrhoea in the 6 months before the index sample	Binary	Univariate	Up to 6 months previous to the sample
4.1.1	If yes, date of sample and result of tests	Number of days between sample and	Univariate	Up to 6 months previous to the sample

		test is		
		Continuous		
		Decult of		
		Result of		
		Catagorical		
12	Did the nationt	Rinary	Univariato	Up to 6 months
4.2	have a diarrhoea	binary	Univariate	after the sample
	enisode in the 6			arter the sumple
	months following			
	the index sample			
4.3	Was the patient	Binary	Univariate	Up to 6 months
	tested for CDI in the	,		after the sample
	6 months following			
	the index sample			
4.3.1	If yes, date of	Number of	Univariate	Up to 6 months
	sample and result	days		after the sample
	of tests	between		
		sample and		
		test is		
		Continuous		
		Result of		
		test is		
		Categorical		
4.4	Was the Clostridium	Binary	Univariate	Patient admission
	difficile sent for	,		when the sample
	ribotyping?			was taken
4.5	Was the severity of	Binary	Univariate	Patient admission

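### CDI-linked death and the CDI-worded help and purchase items depend on local recognition of CDI, so comparing them across countries and settings partly measures local testing

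*SAP*

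**What the plan says.** - **What is promised.** Protocol 3.2.7: "Comparisons will be made between recurrence/Morbidity/Mortality (crude and attributable) rates in different healthcare settings and countries". Attributable is not defined there or in the SAP. The primary outcome in Protocol 3.2.2 is crude mortality at 30 days and 6 months. It includes a comparison of correctly diagnosed patients with "those that were 'missed' (either due to lack of testing or inadequate testing").
- **What is collected.** SAP Appendix 1 asks, for patients who died, whether the "death linked to CDI" applied (10.5.1 at 30 days, 10.7.1 from 30 days to 6 months). Both are binary, with no linkage rule or adjudication. Items 2.7-2.9 record help received while CDI was present and whether there were CDI purchases ("Were any CDI related purchases necessary").
- **Who answers.** Protocol 3.2.6: "The CRF will be completed by the clinical care team at the participating site that submitted the sample". SAP section 2 describes the source as retrospective case notes.
- **What the site is told.** Protocol 5.0: "Results of additional testing will not be reported back to participating laboratories", and "additional COMBACTE-CDI study results will NOT be available for patient management". Protocol 1.4.2 (Data protection) says that sites complete CRFs "on all cases and a proportion of controls (CDI negative samples) identified by the central testing laboratory". It does not say whether the request shows who is a case and who is a control.
- **How it is analysed.** SAP 7.2 sends the Appendix 1 items marked for univariate analysis, including 10.5.1 and 10.7.1, into case-control comparisons and into checks of consistency between countries and settings. The submitting laboratory's own CDI result is collected (Protocol 3.1.6) but plays no part in that analysis.

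**The concern.** The study sets out to find and describe patients with CDI whom local practice missed. For such a patient the notes may contain no mention of CDI, and then the person completing the CRF has little basis for linking a death, a purchase or extra help at home to it. The recorded item is the product of disease and local recognition, and recognition is likely to vary along the axes being compared: country, hospital or community, diagnostic category, and missed or found.

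A country or setting that tests less would record fewer CDI-linked deaths and less CDI-labelled burden even if the disease were identical. WP2 asks whether better guideline compliance lowers burden, and there the bias would run against sites that test well.

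**Working it through.** **1. The plan's own figures.** SAP Table 1 reproduces: cases 103 + 71 + 39 = 213; controls 365 + 147 = 512; total 725; ratio 512/213 = 2.40. The documents give no rate of CDI-linked death and no share of cases missed locally, so everything in steps 3 and 4 rests on assumed values.

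**2. Sorting the items by what a negative answer means in an unrecognised case.**
- *Judgement that needs a CDI label:* 10.5.1, 10.7.1, and 2.7-2.9. A negative may only mean that nobody knew, so these are open to misclassification.
- *Care delivered:* severity graded (4.5), procedures for the CDI episode (5.11), isolation due to CDI (5.16), change or escalation of CDI medication (7.1). An unrecognised patient did not receive these, so a negative is correct. They are valid as records of care but do not measure disease burden in missed cases.
- *No label needed:* all-cause death (10.5, 10.7), discharge and readmission (10.1-10.4, 10.6), diarrhoea duration (5.10), ventilation (5.15). This mechanism does not affect them.

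**3. Size for the first group.** Let *a* be the true CDI-linked death rate, assumed equal in missed and found cases; *m* the share of cases missed locally on the index sample; *s* the share of missed cases recognised later or empirically. Assume the link is recorded whenever CDI was recognised.

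Recorded rate = a(1 - m) + a·m·s, so recorded/true = 1 - m(1 - s).

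| m (assumed) | s = 0 | s = 0.25 | s = 0.5 |
|---|---|---|---|
| 10% | 0.90 | 0.93 | 0.95 |
| 25% | 0.75 | 0.81 | 0.88 |
| 40% | 0.60 | 0.70 | 0.80 |
| 60% | 0.40 | 0.55 | 0.70 |

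With an assumed *a* of 5%, 213 × 0.05 = 10.7 CDI-linked deaths are expected. At m = 25%, 8.0 are recorded if s = 0 and 8.7 if s = 0.25.

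For a comparison, take two countries with the same true rate that recognise 80% and 40% of cases on the index sample (m = 20% and 60%, assumed). The recorded ratio is 0.80/0.40 = 2.0 at s = 0, and (1 - 0.20 × 0.75)/(1 - 0.60 × 0.75) = 0.85/0.55 = 1.55 at s = 0.25. The true ratio is 1.

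If CRF completers can see case status, this formula does not apply. Attribution is then made with knowledge of the central result, and the direction of the error is not fixed.

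**4. What the alternative can detect.** Excess all-cause death over the 512 controls needs no local label. Smallest detectable excess (two-sided 5%, 80% power, unadjusted), in percentage points:

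| Assumed control mortality | 213 cases | 53 missed cases (25% of 213, assumed) |
|---|---|---|
| 5% | 6.0 | 11.1 |
| 10% | 7.7 | 14.0 |
| 15% | 8.9 | 16.0 |

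**The case against.** The strongest reply is that the main results do not depend on these items. Crude mortality is the primary outcome and already includes the missed against correctly diagnosed comparison. Discharge, readmission, diarrhoea duration and laboratory markers are collected without reference to CDI. That stands, and it limits the point to the CDI-labelled items.

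A reader might also draw stronger conclusions, which the documents do not support:

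- *That the items are zero by construction in missed cases.* The CRF is completed six months on. Item 4.3 records CDI tests after the index sample, and Protocol 3.2.1 accepts that a recurrence may be diagnosed empirically or through another laboratory. The CRF request may also reveal case status.
- *That attributable mortality is item 10.5.1 or 10.7.1.* No passage says so. With 512 controls, excess over controls is at least as natural a reading. What can be criticised is that the term is undefined.
- *That the CDI costs are therefore wrong.* Protocol 3.5.4 collects costs by site questionnaire, and 3.5.7 combines micro-costing with published data. Items 2.7-2.9 are not the only source.
- *That the 110 of 213 cases (52%) negative by CCNA show how many were missed.* This is a central-laboratory category. A local gene or culture test may have found some of these patients, and a CCNA-positive sample may never have been tested locally.

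The reply also bears on the remedy. Controls are matched on location only (SAP section 4), so unadjusted excess death would be confounded by age and comorbidity. The local result covers one sample and would misclassify patients recognised by other routes. Both objections are accepted and shape the fix.

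**Conclusion.** The point holds for items 10.5.1, 10.7.1 and 2.7-2.9. Their ascertainment depends on local recognition of CDI, or is unblinded if case status is visible, and SAP 7.2 compares them across countries and settings as if it did not. Part of any difference in CDI-linked death or CDI-labelled burden will therefore reflect local testing. Items 4.5, 5.11, 5.16 and 7.1 are sound as records of care and should only be kept from being read as burden in missed cases.

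The size cannot be known from the documents. The attenuation formula rests on equal true rates in missed and found cases and on full recording once CDI is recognised. If missed cases are truly milder, the shortfall in the pooled rate is smaller. The direction, towards zero in missed cases, is secure only if CRF completers do not know case status. Nothing here undermines the crude mortality outcome. This is a worthwhile and cheap improvement.

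**What to change.** In SAP 7.2 and Appendix 1:

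1. Report 10.5.1, 10.7.1 and 2.7-2.9 stratified by local recognition, derived from the submitting laboratory's result together with later CDI tests (item 4.3) or recorded CDI treatment. Do not use them unstratified to compare countries, settings, diagnostic categories, or missed with found cases.
2. Define attributable mortality as the excess of all-cause death in cases over controls at 30 days and 6 months, adjusted for age and comorbidity, with confidence intervals.
3. For missed cases, take burden from items that need no CDI label (time to discharge, readmission, diarrhoea duration, ventilation), compared with controls. Describe 4.5, 5.11, 5.16 and 7.1 as care delivered.
4. State whether the people completing the CRF know who is a case. If they do, say so when interpreting 10.5.1 and 10.7.1.

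The cost is SAP wording and one derived variable from data already planned for collection. The downside is that CDI-linked death will rest on fewer patients, and excess mortality will be imprecise, especially in missed cases. With an assumed 53 such patients, only an excess of about 11 to 16 points would be detectable, so estimates with intervals are more useful than tests.
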